6.3 Exploratory objectives

7 Statistical methods for safety and tolerability data

All subjects within the safety analysis set will be included in the safety data analysis.

7.1.1 Variables

Adverse events, vital signs (blood pressure, pulse rate, body temperature), ECG intervals, laboratory measurements, immunogenicity, as well as subject demographics, baseline characteristics (including but not limited to prior sarcoidosis immunosuppressant therapy (stratification factor), baseline prednisone dose and mMRC dyspnea scale), and treatment information.

For each women of child bearing potential (WOCBP) the duration (in days) of the total follow-up period will be derived as:

Date of the last assessment - date of the last dosing + 1.

7.1.2 Descriptive analyses

Subject demographics and other baseline characteristics

All data for background and demographic variables will be listed by treatment group and subject. Summary statistics will be provided by treatment group.

Relevant medical history and current medical conditions, results of laboratory screens, will be listed by treatment group and subject.

Treatment

Data for study drug administration (rescue medication) and concomitant therapies will be listed by treatment group and subject.

For each WOCP subject the duration (in days) of the total follow-up period will be listed.

A summary of the steroid dose (prednisone) assigned at the start of the treatment phase and of the prior immunosuppressant therapy will be provided too.

Vital signs

If ranges are available abnormalities will be listed by treatment, subject and visit/time. Summary statistics will be provided by treatment and visit/time. Vital signs collected during the 6MWT will be reported separately.

ECG evaluations

Abnormalities will be listed by treatment, subject and visit/time. Summary statistics will be provided by treatment and visit/time.

Clinical laboratory evaluations

Abnormalities will be listed by treatment, subject and visit/time. A fasting lipid panel will be performed, measuring cholesterol, direct LDL, HDL cholesterol, LDL cholesterol, and triglycerides. Lipid panel parameters and glucose will be summarized only under fasting conditions. For all other lab parameters, the fasting status will be ignored for summary statistics and graphical presentations. Summary statistics will be provided by treatment and visit/time. All data will be included in the listings and the fasting status will be distinguished by a fasting status flag.

Adverse events

Adverse events collected before the start of the study drug and during the pregnancy testing epoch will be listed separately, while treatment emergent adverse events (events with an onset day >= date of the first dosing and <= date of the follow-up phase) will be listed and summarized as described below.

All information obtained on adverse events will be displayed by treatment and subject. The number and percentage of subjects with adverse events will be tabulated by body system and

preferred term with a breakdown by treatment. A subject with multiple adverse events within a body system is only counted once towards the total of this body system and treatment.

The number and percentage of subjects with adverse events of special interest will be summarized by treatment.

AEs of Special Interest comprise hypersensitivity reactions such as serum sickness and anaphylaxis (as defined by Sampson criterion #1; Sampson et al 2006).

Criteria #1	Acute onset of an illness (minutes to several hours) with involvement of the skin, mucosal tissue, or both (eg, generalized hives, pruritus or flushing, swollen lipstongue-uvula)
	AND AT LEAST ONE OF THE FOLLOWING
a.	Respiratory compromise (eg, dyspnea, wheeze-bronchospasm, stridor, reduced PEF, hypoxemia)
b.	Reduced BP or associated symptoms of end-organ dysfunction (eg, hypotonia [collapse], syncope, incontinence)

Commercially Confidential Information

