#### Glossary of terms

Novartis Amended Protocol Version v08 (Clean)

Treatment arm/group	A treatment arm/group defines the dose and regimen or the combination, and may consist of 1 or more cohorts.
Variable	A measured value or assessed response that is determined in specific assessments and used in data analysis to evaluate the drug being tested in the study
Withdrawal of study consent (WoC)	Withdrawal of consent from the study occurs only when a subject does not want to participate in the study any longer and does not allow any further collection of personal data

Protocol summa		
Protocol number	CCMK389X2201	
Full Title	A subject and investigator blinded, randomized, placebo-controlled, repeat- dose, multicenter study to investigate efficacy, safety, and tolerability of CMK389 in patients with chronic pulmonary sarcoidosis	
Brief title	Study of efficacy, safety and tolerability of CMK389 in patients with chronic pulmonary sarcoidosis	
Sponsor and	Novartis	
Clinical Trial Phase	Phase II	
Intervention type	Biologic	
Study type	Interventional	
Purpose and rationale	The purpose of this proof-of-concept study is to determine whether CMK389 displays the safety and efficacy profile to support further development in chronic pulmonary sarcoidosis	
Primary Objective(s)	To assess the efficacy of CMK389 in subjects with chronic pulmonary sarcoidosis by looking at the change from baseline to end-of-treatment (16 weeks of treatment) in forced vital capacity (FVC)	
Secondary Objectives	To assess the impact of CMK389 on a composite index of pulmonary physiology and exercise capacity from baseline to end-of-treatment	
	To assess the safety and tolerability of CMK389 by evaluating adverse events, vital signs and routine safety laboratory results from baseline to end- of treatment	
	To explore the impact of CMK389 observed with [  F]-fluorodeoxyglucose positron emission tomography/computed tomography ([  F]-FDG-PET/CT) imaging (SUVmax and SUVmean) from baseline to week 16	
	To assess the impact of CMK389 on forced expiratory volume in one second (FEV1) and diffusion capacity (DLCO) between baseline and week 16	
	To assess the impact of CMK389 on 6 min walk distance between baseline and week 16	
	To assess the impact of CMK389 on steroid use (mg-days) for each arm between baseline and end-of-treatment	
	To assess the pharmacokinetics of CMK389 after multiple doses in sarcoidosis patients at times specified at doses 1, 2, 3 and 4	

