# 8.6 Safety

Safety assessments are specified below; methods for assessment and recording are specified in the SOM, with the Assessment schedule (Section 8.1) detailing when each assessment is to be performed.

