# 9 Safety monitoring

#### 9.1 Adverse events

An adverse event (AE) is any untoward medical occurrence (i.e., any unfavorable and unintended sign [including abnormal laboratory findings], symptom or disease) in a subject after providing written informed consent for participation in the study until the end of study visit. Therefore, an AE may or may not be temporally or causally associated with the use of a medicinal (investigational) product.

AEs of Special Interest comprise hypersensitivity reactions such as serum sickness and anaphylaxis (as defined by Sampson criterion #1; Sampson et al 2006).

In addition, all reports of intentional misuse and abuse of the study treatment are also considered an adverse event irrespective if a clinical event has occurred. See Section 9.5 for an overview of the reporting requirements.

The occurrence of adverse events must be sought by non-directive questioning of the subject at each visit during the study. Adverse events also may be detected when they are volunteered by the subject during or between visits or through physical examination finding, laboratory test finding, or other assessments.

Abnormal laboratory values or test results constitute adverse events only if they fulfill at least one of the following criteria:

- they induce clinical signs or symptoms,
- they are considered clinically significant,
- they require therapy.

Clinically significant abnormal laboratory values or test results should be identified through a review of values outside of normal ranges/clinically notable ranges, significant changes from baseline or the previous visit, or values which are considered to be non-typical in patients with underlying disease. Investigators have the responsibility for managing the safety of individual subject and identifying adverse events. Alert ranges for liver and kidney related events are included in Appendix 1 and Appendix 2, respectively.

Adverse events should be recorded on the Adverse Events CRF under the signs, symptoms or diagnosis associated with them, and accompanied by the following information:

- 1. The severity grade
  - a. Adverse events will be primarily assessed and graded according to the "Toxicity Grading Scale for Healthy Adult and Adolescent Volunteers Enrolled in Preventive Vaccine Clinical Trials". A copy of the Toxicity Grading Scale can be found in the Investigator Portal.

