b. For any adverse event not listed in the "Toxicity Grading Scale for Healthy Adult and Adolescent Volunteers Enrolled in Preventive Vaccine Clinical Trials", the adverse event will be assessed and graded according to the "Common Terminology Criteria for Adverse Events", version 5.0 (CTCAE v5.0). A copy of the CTCAE Grading Scale can be found in the Investigator Portal.

Confidential

- c. For infusion-related reactions, event will also be assessed and graded according to the CTCAE v5.0
- 2. Its relationship to the study treatment
  - Yes or
  - No
- 3. Its duration (start and end dates) or if the event is ongoing an outcome of not recovered/not resolved must be reported.
- 4. Whether it constitutes a SAE (see Section 9.2 for definition of SAE) and which seriousness criteria have been met
- 5. Action taken regarding investigational treatment.

All adverse events must be treated appropriately. Treatment may include one or more of the following:

- no action taken (e.g. further observation only)
- investigational treatment dosage increased/reduced
- investigational treatment interrupted/withdrawn
- concomitant medication or non-drug therapy given
- hospitalization/prolonged hospitalization (see Section 9.2 for definition of SAE)

Information about common side effects already known about the investigational drug can be found in the Investigator's Brochure (IB) or will be communicated between IB updates in the form of Investigator Notifications. Once an adverse event is detected, it must be followed until its resolution or until it is judged to be permanent, and assessment should be made at each visit (or more frequently, if necessary) of any changes in severity, the suspected relationship to the investigational drug, the interventions required to treat it, and the outcome.

The investigator must also instruct each subject to report any new adverse event (beyond the protocol observation period) that the subject, or the subject's personal physician, believes might reasonably be related to study treatment. This information must be recorded in the investigator's source documents; however, if the AE meets the criteria of an SAE, it must be reported to Novartis.

\*Refer to the Site Operations Manual for data capture methodology regarding AE collection for subjects that fail screening.

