# 9.2 Serious adverse event reporting

# 9.2.1 Definition of SAE

An SAE is defined as any adverse event (appearance of (or worsening of any pre-existing) undesirable sign(s), symptom(s) or medical conditions(s)) which meets any one of the following criteria:

- is fatal or life-threatening
- results in persistent or significant disability/incapacity
- constitutes a congenital anomaly/birth defect
- requires inpatient hospitalization or prolongation of existing hospitalization, unless hospitalization is for:
  - routine treatment or monitoring of the studied indication, not associated with any deterioration in condition
  - elective or pre-planned treatment for a pre-existing condition that is unrelated to the indication under study and has not worsened since the start of study drug
  - treatment on an emergency outpatient basis for an event not fulfilling any of the definitions of a SAE given above and not resulting in hospital admission
  - social reasons and respite care in the absence of any deterioration in the subject's general condition
- is medically significant, e.g. defined as an event that jeopardizes the subject or may require medical or surgical intervention.

All malignant neoplasms will be assessed as serious under "medically significant" if other seriousness criteria are not met.

Life-threatening in the context of a SAE refers to a reaction in which the subject was at risk of death at the time of the reaction; it does not refer to a reaction that hypothetically might have caused death if it were more severe (please refer to ICH E2D Guideline 2004).

Medical and scientific judgment should be exercised in deciding whether other situations should be considered serious reactions, such as important medical events that might not be immediately life threatening or result in death or hospitalization but might jeopardize the subject or might require intervention to prevent one of the other outcomes listed above. Examples of such events are intensive treatment in an emergency room or at home for allergic bronchospasm, blood dyscrasias or convulsions that do not result in hospitalization or development of dependency or abuse (please refer to ICH E2D Guideline 2004).

Any suspected transmission via a medicinal product of an infectious agent is also considered a serious adverse reaction.

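### The SAP defines treatment-emergent adverse events by onset day alone, so a pre-dose event that worsens after dosing is not tabulated when it keeps its original onset date

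*SAP*

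**What the plan says.** SAP Section 7.1.2 sorts adverse events into two groups. The first is set apart: "Adverse events collected before the start of the study drug and during the pregnancy testing epoch will be listed separately". The second is listed and also summarised by body system, preferred term and treatment: "treatment emergent adverse events (events with an onset day >= date of the first dosing and <= date of the follow-up phase"). The test is the onset day, and nothing in the section refers to worsening.

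The protocol collects more than this rule uses:

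- Section 9.1 defines an adverse event as one occurring "in a subject after providing written informed consent for participation in the study until the end of study visit", so screening and run-in events are captured.
- Once an event is detected, Section 9.1 says "assessment should be made at each visit (or more frequently, if necessary) of any changes in severity".
- The SAE definition in Section 9.2.1 covers "appearance of (or worsening of any pre-existing) undesirable sign(s), symptom(s) or medical conditions(s"), provided a seriousness criterion is also met.
- Section 11.4.4 plans adverse event tables by treatment with no treatment-emergent restriction.

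**The concern.** A common purpose of a treatment-emergent definition is to capture both new events and existing events that become worse on treatment. The SAP rule captures only the first kind.

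The gap matters more here than in a trial with a short, quiet screening period. Before the first dose, every patient stops methotrexate or azathioprine and enters the steroid titration algorithm, so some events ongoing at Day 1 are plausible. Safety and tolerability is a secondary objective, and the by-arm adverse event tables are the main comparative safety output of a trial of about 66 patients. An event whose severity rises after dosing is information those tables should carry.

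**Working it through.** **Inputs.** The rule is in SAP 7.1.2. The collection window is in Protocol 9.1. The nominal visit days are in Protocol Table 8-1: screening Day -70 to -43, V101 Day -42, V102 Day -28, V201 Day 1, V202 Day 29, V299 Day 113, V399 Day 197. About 66 patients are randomised 1:1 (Protocol 3.1).

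**1. Reproduce the plan's own durations.** Safety follow-up: 197 - 113 = 84 days; 84 / 7 = 12.0 weeks, as Protocol 3.1 states. Run-in: with no Day 0, Day -42 to Day 1 is 42 days; 42 / 7 = 6.0 weeks, also as stated.

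**2. Length of the pre-dose collection period.** On the same day count, Day -70 or Day -43 to Day 1 is 70 or 43 days. Immunosuppressant withdrawal falls 42 days before the first dose and the start of steroid titration 28 days before it. Both lie inside the period.

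**3. Apply the rule to four cases, using visit days as examples.**

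| Event | Onset on record | Listed | Tabulated |
|---|---|---|---|
| New at Day 29 | Day 29 | Yes | Yes |
| Starts Day -28, resolves before Day 1 | Day -28 | Yes | No (rightly) |
| Starts Day -28, more severe from Day 29, one record | Day -28 | Yes | **No** |
| Same course, new record opened at worsening | Day 29 | Yes | Yes |

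Only the third row is a defect, and it depends on how the worsening is recorded.

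**4. What the protocol says about recording.** Section 9.1 gives each event one duration, with a start and an end date. It then has the event followed to resolution, with "any changes in severity, the suspected relationship to the investigational drug" reassessed at each visit. That describes one record under its original start date. Section 9.2.2 has progression of an SAE reported as follow-up to the original event, although it also asks for a separate report when an SAE occurs at a different time interval. The detail is delegated: Section 8.6 says "methods for assessment and recording are specified in the SOM". The protocol text therefore points towards the third row without settling it.

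**5. Does the Day 1 entry check remove these patients?** Not fully. By Figure 3-2, a deteriorating status needs at least two parameters worse, or an mMRC change of at least 2 points. A patient one mMRC point worse with the other parameters unchanged is classed as stable and is dosed. Adverse events outside the four parameters play no part in the check.

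**6. Size.** The documents give no rate of ongoing run-in events and no rate of worsening, so the number affected cannot be computed. What can be said is the weight of one patient: 66 / 2 = 33 per arm, and 1 / 33 = 3.0 percentage points in a table row.

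**The case against.** The strongest reply is that the rule may work properly once the operational documents are read with it. Recording is left to the Site Operations Manual, and SAP 1.1 places derived-variable rules in a separate programming specification. Neither is available here. If sites open a new record when an event worsens, that record has a post-dose onset and is counted. This stands. A reader might infer that worsened events can never reach the tables, and the documents do not support that.

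Second, respiratory worsening is summarised elsewhere. SAP 6.2.2 tabulates by arm the clinical status components (including dyspnoea), deterioration at Weeks 4 to 16, and any steroid increase. This stands in part. Those outputs belong to the PD section and its analysis set, and they do not cover worsening of other kinds of event.

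Third, pre-dose events are still listed, and 66 patients can be reviewed by hand. That is true, but a listing does not give a comparison by arm.

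A reader might also infer that the end date, loosely worded as a phase, cuts the tables off at the start of follow-up (Day 113). That would lose 84 of 197 - 1 = 196 days after the first dose (43%). The documents do not support this reading. The same sentence sets aside only pre-dose and pregnancy-testing events, so a Day 113 limit would leave events from Day 114 to Day 197 in neither group, although they are collected. The Protocol summary does mention "routine safety laboratory results from baseline to end- of treatment", but that is an abbreviated objective. The objectives tables in Protocol 2.2 and SAP 1.3.2 carry no such limit. The natural end is V399.

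**Conclusion.** The point holds in a limited form. The SAP's definition uses onset day only, so an event that began between consent and first dose, and increased in severity after first dose, is listed but not counted when it is kept under its original onset date. The protocol's description of following one event over time makes that outcome likely enough to settle now, but it rests on the assumption that no new record is opened.

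The rule is the same in both arms, and both go through the same run-in. A reader might infer that it hides harm from CMK389 in particular; the documents show no differential effect. Nor does the protocol treat every worsening as an SAE, since a seriousness criterion must also be met. The number of patients affected is unknown. The primary and other efficacy analyses are untouched. The end-date wording needs clarification only.

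**What to change.** In SAP 7.1.2, define a treatment-emergent adverse event as one with onset on or after the first dose, or one present before the first dose that increases in severity after it. Confirm that the adverse event record captures the date of worsening, or that sites open a new record when a pre-dose event worsens. If neither is in the Site Operations Manual, add a line of CRF guidance.

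As a clarification, state the end of the window as the end of the safety follow-up epoch (EOS#1, V399), or the last safety contact if that is earlier, which also covers patients who stop early.

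The cost is about one sentence in the SAP and at most one line of site guidance. The small downside is slightly higher treatment-emergent counts in both arms.
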